Objectives:	 Part 1 is a randomized, double-blind, crossover, dose-escalation, placebo-controlled study in 28 healthy adult subjects with the following objectives: Primary: To evaluate the effect of oral LQT-1213 on dofetilide-induced QT interval corrected for heart rate (HR; QTc) prolongation in healthy adult subjects Secondary: To evaluate the safety and tolerability of a combination of oral dofetilide and oral LQT-1213 in healthy adults Secondary: To determine the pharmacokinetics (PK) of oral LQT-1213 and oral dofetilide in healthy adults Part 2 is a single-blind, multiple-dose study in up to 12 adult participants with Long QT Syndrome Type 2 (LQT/LQTS 2) and in up to 12 adult participants with Long QT Syndrome Type 3 (LQT/LQTS 3) with the following objectives: Primary: To evaluate the safety and tolerability of oral LQT-1213 in participants with LQT2 or LQT3 Secondary: To determine the PK of oral LQT-1213 in participants with LQT2 or LQT3 Exploratory: To evaluate the correlation between the PK of LQT-1213 and candidate serum- and glucocorticoid-regulated kinase-1 (SGK-1) protein targets in participant peripheral blood mononuclear cells (PBMCs) in order to derive PK/pharmacodynamic (PD) relationships between drug
	exposure and target engagement; additional exploratory PD endpoints may be assessed
Endpoints:	Part 1: Pharmacodynamic: The primary analysis will be the time-based comparison in the change from baseline (baseline defined as the Day 1 of Period 1 and Day 1 of Period 2 mean predose QTc) QTc by Fridericia's formula (QTcF) during approximate peak dofetilide exposure as detailed in the statistical analysis plan (SAP) between dofetilide and placebo treatment, and the dofetilide and LQT-1213 treatment on Day 8 of each period with secondary endpoints on Days 4 and 6 of each period. If a substantial HR effect is observed, other correction methods such as QTc with individual correction (QTcI) and QTc with population correction

(QTcP) will be explored and compared, as will be detailed in the SAP. The primary correction method will be the one that removes the HR dependence of the QT interval most efficiently.

Primary pharmacodynamic endpoints:

- Dofetilide/placebo-corrected ΔQTcF (ΔΔQTcF)
- Dofetilide/placebo-corrected ΔQTcI or ΔQTcP (ΔΔQTcI, ΔΔQTcP) if used as the primary correction method if a substantial HR effect is observed

Secondary pharmacodynamic endpoints:

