Electrocardiogram and QT/QTc Analyses: The analysis will be described in the SAP. All QTc data will represent the means of the extracted QTc intervals, based on ECGs extracted from the Holters at the defined time points. Each individual QT and time elapsed between 2 successive R waves of the QRS signal on the ECG (RR) interval will be used to calculate a QTc interval. The individual QTc intervals will then be averaged for analysis. Baseline will be defined as the mean of the triplicate ECG data collected predose for each period.

Fridericia's formula will be the default correction method for QT intervals to remove HR dependence.

If the QTcF is not an adequate correction, other methods will be reviewed. For each method tested (including Fridericia's correction), the relationship between the QTc and RR will be evaluated with a linear-regression model. Mean QTc and RR values at all nominal time points will be used. The model with the slope closest to zero will be selected as the primary QTc endpoint. The additional correction methods and definition of an adequate correction will be detailed in the SAP.

A statistical analysis will be performed per ICH E14 guidance using the appropriate population and will be detailed in the SAP. The specifics of the concentration-QTc and categorical analyses will be detailed in the SAP.

Pharmacokinetics: The analysis will be detailed in the SAP which will be finalized before database lock. Data will be listed and summarized, where applicable. Plasma concentrations of dofetilide and LQT-1213 will be listed and summarized by treatment for each sample time point using descriptive statistics. Mean and individual plasma dofetilide and LQT-1213 concentration-time profiles will be presented in figures on linear and semilogarithmic scales. Assessment of a drug interaction between dofetilide and LQT-1213 will be examined.

Safety: Safety data including reported AEs, clinical laboratory assessments, vital signs measurements, and safety 12-lead ECGs will be summarized. Physical examination findings will be listed.

Part 2:

Safety: Safety data including reported AEs, clinical laboratory assessments, vital signs measurements, continuous telemetry ECG monitoring, and safety 12-lead ECGs will be summarized. Physical examination findings will be listed.

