Pharmacokinetics: The analysis will be detailed in the SAP which will be finalized before database lock. Data will be listed and summarized, where applicable. Plasma concentrations of LQT-1213 will be listed and summarized by LQT subtype for each sample time point using descriptive statistics. Mean and individual LQT-1213 concentration-time profiles will be presented in figures on linear and semilogarithmic scales. Pharmacokinetics/Pharmacodynamics: Details of the potential PD (SGK-1 protein targets) analyses to derive PK (LQT-1213)/PD relationships between drug exposure and target engagement will be provided in a separate analysis plan.

Sample size:	Part 1: Based on the calculation of the sample size for a Thorough QT study (Zhang and Machado, 2008), as the test is performed at 5 time points separately, a 1 sided 5% significance level (with adjusted 1-sided significance levels of 5%, 2.5%, 1.67%, 1.25%, and 1%) is used along with a within-subject SD of 8 ms for ΔQTcF for all treatment groups. A sample size of 20 evaluable subjects in a crossover design who complete the study will provide a power of 90% to detect 7 ms QTc effect, ie, the lower bound of all the 2 sided 90% CIs on ΔΔQTcF will exceed 7 ms at least 1 of the 5 prespecified time points. Multiplicity will be controlled by using a Hochberg procedure (Hochberg 1988). Twenty-eight subjects will be enrolled to account for dropouts.
	Part 2: In this exploratory safety study, up to 12 participants with LQT2 and up to 12 participants with LQT3 will be recruited. The sample size was not estimated based on statistical considerations but was considered sufficient to achieve the primary safety objectives of the study.
Date of protocol:	05 December 2023

2. List of Abbreviations

Abbreviation	Definition
ΔΔΗR	time-matched, placebo-adjusted, change from baseline in HR
$\Delta\Delta QRS$	time-matched, placebo-adjusted, change from baseline in QRS
ΔΔQΤc	time-matched, placebo-adjusted, change from baseline in QTc
$\Delta\Delta QTcF$	time-matched, placebo-adjusted, change from baseline in QTcF
$\Delta\Delta PR$	time-matched, placebo-adjusted, change from baseline in PR
Δ HR	change from baseline in heart rate
ΔQRS	change from baseline in QRS
ΔQTc	change from baseline in QTc
$\Delta QTcF$	change from baseline in QTcF
$\Delta QTcI$	change from baseline in QTcI
$\Delta QTcP$	change from baseline in QTcP
ΔPR	change from baseline in PR interval
λ_{z}	apparent terminal rate constant

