5.7.1.3. Categorical Analyses

5.7.1.3.1 Part 1

Categorical analyses of QTc, PR, QRS, and HR will be provided to determine the number and percentage of subjects, by treatment, who meet the following criteria overall and at each time point:

- QTc results >450 and ≤ 480 , >480 and ≤ 500 , and >500 ms
- \triangle QTc from baseline >30 and \leq 60, and >60 ms
- ΔQTc from dofetilide/placebo reduction of >10, >15, >20, >25, >30, and >40 ms
- PR outliers (PR >200 ms and a 25% or greater increase from baseline)
- QRS outliers (QRS >120 ms and a 25% or greater increase from baseline)
- HR outliers (HR <50 bpm and a 25% or greater decrease from baseline)
- HR outliers (HR >100 bpm and a 25% or greater increase from baseline)

5.7.1.3.2 Part 2

None planned.

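### The Part 1 sample-size sentence in the synopsis uses 7 ms as both the powered effect and the confidence bound; at a true 7 ms the written criterion succeeds in about 3–5% of trials under Hochberg, not 90%

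*Protocol*

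**What the plan says.** The Part 1 entry under Sample size in the Protocol synopsis (Section 1) states that 20 evaluable crossover subjects "will provide a power of 90% to detect 7 ms QTc effect". Linked by *ie*, it explains this as "the lower bound of all the 2 sided 90% CIs on ΔΔQTcF will exceed 7 ms" at "at least 1 of the 5 prespecified time points". The variability input is "a within-subject SD of 8 ms for ΔQTcF for all treatment groups". The test is one-sided at 5%, with adjusted levels of 5%, 2.5%, 1.67%, 1.25% and 1%, and "Multiplicity will be controlled by using a Hochberg procedure". Enrolment is 28 to allow for dropouts.

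Other places bear on how far the sentence can be read:

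- The synopsis statistical methods defer the detail: "A statistical analysis will be performed per ICH E14 guidance using the appropriate population and will be detailed in the SAP".
- Protocol Section 5.6.1.1, the body section on Part 1 sample size, shows only its heading in this copy.
- Protocol Section 5.7 gives each part its own SAP. The supplied SAP (Section 3) refers Part 1 to a separate plan, which was not supplied.
- Protocol Section 5.7.1.3.1 counts benefit as a positive number, "from dofetilide/placebo reduction of >10, >15, >20, >25, >30, and >40 ms", so a positive lower bound can be read as a reduction in QTc. The synopsis does not spell this direction out.

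**The concern.** A power statement needs two numbers: the bound that the data must exclude, and a true effect lying beyond it. Here both are 7 ms. When the truth sits on the bound, each two-sided 90% interval clears it 5% of the time, whatever the sample size or SD, so 90% cannot hold for the criterion as written.

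In the readable text this is the only numerical success threshold for the Part 1 primary endpoint, and it carries the justification for 20 evaluable subjects. Excluding 0 ms and excluding 7 ms are different claims about the drug, and one result can pass the first and fail the second.

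Two further wording problems sit in the same sentence. It asks for all the intervals and also for one or more of five. It also pairs plain 90% intervals (one-sided 5%) with Hochberg levels that go down to 1%.

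**Working it through.** **Inputs from the synopsis.** n = 20; SD 8 ms; effect 7 ms; written bound 7 ms; five time points; one-sided 5% with Hochberg. **Assumed, because not given:** the correlation between time points (0 to 0.9, exchangeable) and how many time points carry the effect.

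**Standard error of the mean difference.**
- 8 ms as the SD of the paired difference: 8/√20 = 1.789 ms.
- 8 ms as the within-subject SD of each treatment's ΔQTcF (the label used): 8 × √(2/20) = 2.530 ms.

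**Formula for one time point.** Power = P(T > t(1−α, df)), where T is noncentral t with noncentrality (true effect − bound)/SE. With two sequences, df = 18. Multi-time-point figures are simulated (60,000 trials per cell, 10 subjects per sequence, 18 df).

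**Step 1: reproduce the 90%, using 7 ms against a bound of 0.**
- Paired-difference SD: noncentrality 7/1.789 = 3.91; power 90.1% at one-sided 1% (90.3% with 19 df).
- Within-subject SD: noncentrality 7/2.530 = 2.77; power 84.5% at 5% and 59.2% at 1%.

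With Hochberg and 7 ms at all five time points:

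| Assumed correlation | 0 | 0.3 | 0.5 | 0.7 | 0.9 |
|---|---|---|---|---|---|
| Within-subject SD 8 | 99.1% | 95.2% | 91.3% | 85.3% | 78.6% |
| Paired-difference SD 8 | 100.0% | 99.9% | 99.6% | 98.8% | 97.2% |

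On the within-subject SD with fewer affected time points: four of five give 97.5%, 94.4% and 92.7% at correlation 0, 0.2 and 0.3; three of five give 93.7%, 91.9% and 90.2% at 0, 0.1 and 0.2; one of five gives about 60%.

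The 90% is therefore reachable on either reading of the SD, provided the bound is 0.

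**Step 2: the criterion as written, bound 7 and true effect 7 at all five time points.** The noncentrality is (7 − 7)/SE = 0, so one interval succeeds 5% of the time on either SD.

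| Assumed correlation | 0 | 0.3 | 0.5 | 0.7 | 0.9 |
|---|---|---|---|---|---|
| Hochberg | 4.9% | 4.6% | 4.1% | 3.5% | 2.7% |
| Unadjusted, one or more of five | 22.6% | 19.7% | 16.8% | 13.8% | 9.5% |
| All five intervals | 0.0% | 0.0% | 0.1% | 0.6% | 1.8% |

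Check for independent time points: 1 − 0.95⁵ = 22.6%. At perfect correlation all three rows become 5%.

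**Step 3: what a 7 ms bound would need for 90% power.** With Hochberg and the effect at all five time points, for correlation 0, 0.5 and 0.9:
- Paired-difference SD: true effect 10.8, 11.9 and 12.8 ms.
- Within-subject SD: true effect 12.4, 13.9 and 15.2 ms.

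At a single time point at one-sided 1%, the true effect needed is 14.0 ms (paired-difference SD) or 16.9 ms (within-subject SD).

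**Step 4: where the two bounds disagree.** This illustration takes one time point and an unadjusted 90% interval. With t(0.95, 18) = 1.734, the half-widths are 1.734 × 1.789 = 3.10 ms and 1.734 × 2.530 = 4.39 ms. An observed reduction between 3.1 and 7 + 3.1 = 10.1 ms (paired-difference SD), or between 4.4 and 7 + 4.4 = 11.4 ms (within-subject SD), excludes 0 but not 7.

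**Dropout allowance.** 28 × (1 − 8/28) = 20, which is consistent.

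**The case against.** The strongest reply is that nothing is miscalculated. Both n = 20 and 90% come out under ordinary readings, including the protocol's own SD label and multiplicity rule (91% at correlation 0.5), and success at the null boundary is just the significance level, which says nothing about this trial's size. That stands: the fault lies in the written criterion, and the 3–5% should not be read as this trial's real power.

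The missing assumption may also be stated elsewhere. Section 5.6.1.1 is unreadable here, the Part 1 SAP was not supplied, and the synopsis defers the primary analysis to that SAP. This stands too, and it limits the point to the synopsis sentence. Even so, a correct SAP would leave that sentence contradicting itself.

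Finally, all the intervals at 90% may be a compressed version of Hochberg's first step, in which all five hypotheses are rejected if every one passes at 5%. That is plausible, so the phrase should be reconciled with the SAP and not simply struck out.

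A reader might infer more than the documents support:

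- **That the trial is underpowered or 20 is too few.** Step 1 shows otherwise for a bound of 0.
- **That labelling 8 ms as within-subject refutes the 90%.** The single-test figures of 84.5% and 59.2% do not apply the stated Hochberg rule at one or more of five.
- **That 90% then needs the effect at all five time points.** Four or three affected time points also reach it at low correlation.
- **That chance success at 7 ms is as high as 23%.** That figure needs unadjusted intervals and independent time points, and the paragraph specifies Hochberg.

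**Conclusion.** The point holds for the synopsis sentence. As written, it claims 90% power for a criterion that, at its only stated effect, is met in about 3–5% of trials under Hochberg. This assumes 7 ms at all five time points and correlation between 0 and 0.9. If some time points have smaller effects, the figure is lower.

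The sentence leaves two materially different rules open: a bound of 0 with a true effect of 7 ms, or a bound of 7 ms with an unstated true effect of about 11–15 ms under Hochberg, depending on SD and correlation. The readable text does not say which was meant. It also does not settle whether 8 ms is a within-subject or a paired-difference SD. If within-subject, the 90% depends on a correlation and a number of affected time points that are not given.

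**What to change.** Take the null bound, the assumed true effect and the success rule from the prespecified Part 1 SAP, and state the bound and the true effect as two separate numbers.

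- If the rule tests against 0, change the synopsis bound from 7 ms to 0 ms, expressed as a reduction, at one or more of the five time points under Hochberg, with power quoted for a true 7 ms reduction.
- If the rule uses a 7 ms bound, keep it and state the larger true effect on which the 90% rests.
- Say whether 8 ms is the within-subject SD or the SD of the paired difference. If within-subject, give the assumed correlation and number of affected time points, and restate the power if it changes.
- Reconcile all the intervals, one or more of five, and the Hochberg levels according to the same SAP rule.

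Keep 20 evaluable subjects and choose no new threshold. Protocol Section 3.6.2 already cites Part 1 safety data, so record the change as a dated wording correction traced to the Part 1 SAP; otherwise it could look like a bound chosen after the results. The cost is one paragraph and one document check, with no added subjects, and possibly a revised power figure if 8 ms proves to be the within-subject SD.

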3.1. Background

Congenital Long QT syndrome (LQTS) is a rare cardiac disorder most commonly caused by mutations in 1 of 3 genes that encode for ion channels involved in ventricular repolarization. Changes in the function of these ion channels result in ventricular action potential duration (APD) prolongation and prolongation of the QT interval corrected for heart rate (HR; QTc) interval, which can precipitate the ventricular arrhythmia Torsades de Pointes, which can lead to fainting, seizures, ventricular fibrillation, and sudden death. LQTS can also occur as the result of adverse effects of drugs and/or electrolyte abnormalities that inhibit the hERG (referred to as acquired LQTS).

Serum- and glucocorticoid-regulated kinase 1 (SGK-1) is a serine-threonine kinase that is under acute transcriptional control by several stimuli, including serum and glucocorticoids. SGK-1 is activated both by insulin and growth factor signaling. Baseline SGK-1 activity is low in cardiomyocytes but is upregulated in pathological states. SGK-1 plays a critical role in the regulation of the voltage-gated sodium channel Nav1.5 in cardiomyocytes by direct phosphorylation as well as regulation of interacting proteins (Bezzerides et al 2017). Activation of SGK-1 in the heart causes an increase in the late sodium current leading to prolongation of the APD, while genetic inhibition of the gene coding for SGK-1 reduces the increase in APD seen with both cardiac stressors and in inherited arrhythmia syndromes in animal models (Das et al 2012, Bapat et al 2021) and cell culture models (Bezzerides et al 2017), respectively. SGK-1 inhibition has been shown to reduce the APD in human-induced pluripotent stem cell-derived cardiomyocytes (hiPSC-CMs) from patients with several types of inherited arrhythmia syndromes such as LQT1 (potassium voltage-gated channel subfamily Q member 1 [KCNQ1] potassium channel locus; loss of function), LQT2 (potassium voltage-gated channel subfamily H member 2 [KCNH2] potassium channel locus; loss of function), and LQT3 (sodium voltage-gated channel alpha subunit 5 [SCN5A] sodium channel locus; gain of function) (Bezzerides et al 2017), as well as acquired LQTS in hiPSC-CMs treated with anemonia viridis toxin II or dofetilide and a guinea pig Langendorff model treated with dofetilide (Kim et al 2023).

Beta-blockers are prescribed as first line therapy for congenital LQTS. This approach reduces autonomic triggers and the probability of Torsades de Pointes but does not address the underlying pathology of prolonged ventricular repolarization, and breakthrough episodes are not uncommon. Beta-blockers are prescribed most commonly to patients with LQT1 mutations and, less commonly, to patients with LQT2 mutations. However, beta-blockers have not been demonstrated to be effective in patients with LQT3 mutations (Han et al 2020). Compliance with beta-blocker therapy is limited by unpleasant side effects including lethargy, dizziness, weight gain, and nausea, and patients often do not comply with dosing recommendations. In certain patients, failure

of beta-blocker therapy is followed by the use of an implantable cardiac defibrillator (ICD).

Thryv Therapeutics Inc. is developing LQT-1213, a potent and selective small molecule drug that inhibits the activity of SGK-1, for the treatment of individuals with congenital or acquired LQTS. In a study of 44,496 Caucasian infants, the prevalence of LQTS was estimated to be 1:2,534 (Schwartz et al 2009). Of these patients, it is estimated that 60% have LQT1, 32% have LQT2, and 8% have LQT3 (Priori et al 2003). Inhibition of SGK-1 inhibition by LQT-1213 likely prevents SGK-1 activity on the late sodium channel current, modulating the late sodium current (including the mutant channel seen in LQT3) and possibly impacting cardiac calcium handling. Multiple preclinical data in hiPSC-CMs bearing LQT2 (KCNH2) and LQT3 (SCN5A) mutations, hiPSC-CMs sheets with KCNH2 mutations, a rabbit heart with a KCNH2 mutations, normal hiPSC-CMs treated with anemone toxin II (mimicking LQT3) and experiments using dofetilide, a hERG blocker, have shown that SGK-1 inhibition shortens or normalizes the prolonged APD. Thus, it is reasonable to evaluate the effects of LQT-1213 in patients with LQTS 2 or 3.

3.2. Summary of LQT-1213 Nonclinical Development

A comprehensive program of in vitro and in vivo nonclinical studies has been completed or is in progress to investigate the primary, secondary, and safety pharmacology, pharmacokinetics (PK), general toxicity, and genotoxicity of LQT-1213 in-line with current International Council on Harmonisation (ICH) and Good Laboratory Practice (GLP) regulatory guidance. Results from these studies are briefly described in this section; additional details can be found in the investigator's brochure.

In vitro studies were conducted to demonstrate the inhibitory effect of LQT-1213 on SGK-1, and the subsequent ability to inhibit APD. LQT-1213 was screened in biochemical and whole cell assays, where LQT-1213 inhibited SGK-1 with half-maximal inhibitory concentration (IC₅₀) values of 0.25 and 89 Nm, respectively. There was no effect of different concentrations of serum protein on LQT-1213 potency against SGK-1.

In cellular assays in hiPSC-CMs bearing LQT1 (V254M-KCNQ1), LQT2 (G604S-KCNH2), and LQT3 (P1332L-SCN5A) mutations, LQT-1213 markedly reduced the prolonged APD in all hiPSC-CMs cells. LQT-1213 additionally inhibited the prolongation of APD induced by treatment with anemonia viridis toxin II (a model for LQT3) or dofetilide (a specific hERG blocker and a model for LQT2) in both hiPSC-CMs (CRISPR/Cas-9 corrected P1332L isogenic line) and normal induced pluripotent stem cell-derived cardiomyocytes (unmodified by CRISPR/Cas-9). The in vivo efficacy of SGK-1 has not been evaluated in animal models of congenital LQTS (caused by ion channel mutations) as the available animal models are either not well-characterized, not translatable to human disease, or not accessible. Note that traditional models, such as heterologous systems, are considered to be incapable of completely recapitulating genetic and phenotypic

features of LQTS, while animal models, particularly in rodents, have electrophysiological characteristics that are often species-specific and different from humans (Sala et al 2019). This hampers the possibility of promptly translating results obtained in vitro directly to the clinics, with significant delays occurring between the discovery of promising treatments and their clinical application. However, the sponsor has shown that LQT-1213 reduced dofetilide-induced QTc prolongation (a model for LQT 2) in Langendorff-perfused guinea pigs and in vivo in dogs.

In secondary pharmacology studies, at presumed supratherapeutic exposures, LQT-1213 demonstrated antagonistic activity toward adrenergic receptors α1A, α1B, α1D, and α2B; AKT3; the calcium channel L-type; nicotinic acetylcholine receptor α3β4; and serotonin receptor 5HT2B, and had agonistic activity toward serotonin receptor 5HT1A. Half-maximal inhibitory concentration/half-maximal inhibitory effective concentration for these receptors were greater than 400 times the IC50 of free LQT-1213 against its target, SGK-1. Clinically significant central tendency effects on blood pressure or orthostatic blood pressure were not observed in the healthy volunteer single-ascending dose/multiple-ascending dose study.

In vitro safety pharmacology findings indicated that LQT-1213 was found to be a weak inhibitor of hERG channel (IC₅₀ 3.38 μM; given 99% human protein binding the margin between the hERG IC₅₀ and the LQT-1213 free fraction at the inhibitory exposure of the SGK-1 IC₅₀ (89 nM is >3500 times). No significant inhibitory effects were observed against the other cardiac ion channels evaluated (hCav1.2, hKir6.2/SUR2A, hKv1.5, hKv4.3/KchiP2.2, and hNav1.5), with the exception of a mild potentiating effect on Nav1.5 channel currents at high supratherapeutic exposures.

In PK studies in mouse, rat, dog, and monkey, LQT-1213 was rapidly absorbed following oral administration with the fastest absorption in rodents (mouse and rat) followed by dog and monkey (time to the maximum observed plasma concentration $[T_{max}] < 1$ h).

Bioavailability was low to moderate in mouse, rat, and dog (22.2%, 17.9-24.0%, and 14.0%, respectively) and lower in monkey (2.88 to 3.01%), consistent with findings of low permeability in Caco-2 and Madin-Darby canine kidney II cells. Volume of distribution at steady state values was slightly greater than total body water (0.91-1.57 L/kg), suggesting distribution to tissues. LQT-1213 partitioned primarily into plasma (blood:plasma ratio of 0.74). LQT-1213 demonstrated high plasma protein binding in human and variable, moderate-to-high binding in nonclinical species.

LQT-1213 demonstrated very high metabolic stability in hepatocytes, liver and intestinal microsomes, S9 liver fractions, plasma, and whole blood. No unique human metabolites were identified in studies in liver microsomes or hepatocytes. Based on cytochrome P450 (CYP) induction and inhibition studies as well as transporter studies, there appears to be limited potential for LQT-1213 to be involved in drug-drug interactions.

Repeat-dose studies were conducted to evaluate the potential toxicity of LQT-1213 in Sprague Dawley rats and Beagle dogs in studies of up to 14-day durations. LQT-1213

was well tolerated in 7-day studies in rats and dogs at doses up to 300 mg/kg/day and 100 mg/kg/day, respectively, which were the highest doses administered and considered to be the no-observed-adverse-effect levels (NOAELs) for each study. Fourteen-day GLP studies in both rats and dogs were conducted using twice daily (BID) administration. LQT-1213 was well tolerated over 14 days of BID dosing in both rats and dogs at doses up to 300 mg/kg/day and 100 mg/kg/day, respectively. At the high dose of 100 mg/kg/day in dogs, sporadic emesis was observed in both male and female animals. Decreases in body weight and food consumption as well as slight changes in clinical pathology parameters (increases in white blood cell parameters [neutrophils, monocytes], bilirubin [rat], urea nitrogen and urine volume and decreases in total protein and albumin [rat] and urine specific gravity [dog]) were observed in both rats and dogs; however, these findings were typically minimal in severity, were reversible following the recovery period, and were not considered adverse.

The 3-month repeat dose GLP toxicology studies in dogs and rats is underway. The total daily doses in these studies are 10, 30 and 100mg/kg in dogs (BID) and 30mg, 100mg and 300mg/kg in rats (BID). The dosing and recovery phases have been completed. Elevations in liver enzymes (ALT, AST, ALP and GGT) and total bilirubin were observed at the end of the dosing phase (Day 92) in the preliminary and unaudited results for the study in dogs at the highest dose of 100mg/kg/day with smaller elevations in ALT at the 30mg/kg/day dose in one dog, compared to control animals. These elevations were reversible in the recovery phase (Day 119). Preliminary results from the study in rats did not show elevations in these enzymes or total bilirubin.

No evidence of genotoxicity has been observed with LQT-1213 in non-GLP and GLP bacterial reverse mutation studies in Salmonella typhimurium or Escherichia coli strains, in a non-GLP in vitro micronucleus assay in Chinese hamster ovary cells, or in a GLP in vivo rat micronucleus assay.

